7.3 Monitoring by the sponsor

7.3.1 Monitoring

All clinical work conducted under this protocol is subject to Good Clinical Practice (GCP) rules, and this may include inspection by the study monitor and/or Ethical Review Committee of ICDDR,B at any time. The investigators agree to the inspection of study-related records by the study monitor and/or Ethical Review Committee of ICDDR,B. The investigator must adhere to the following principles in addition to any applicable local regulations.

7.3.2 Investigational product control

Appropriate case report forms (CRFs) will be developed for recording of study data. Data of medical history, physical examination, laboratory values, and X-ray findings will be transcribed from printouts or patient files (source data) onto the CRF. All raw data including patient's files, laboratory results and radiographs will be considered as "source data", and will be retained in a secure place.

7.4 Documentation

Correspondence (e.g. with sponsors, Ethics Committee) relating to this clinical study will be kept in appropriate file folders. This includes appropriate records of telephone conversations, Email, faxes, and letter correspondence. Records of patients, source documents, CRFs, and drug inventory pertaining to the study must be kept on file. Records must be retained for a period of 15 years. Bayer must be notified at the end of the 15-year period before data can be moved or destroyed. Bayer will clarify if storage needs to be retained in accordance with the longer ICH retention data requirements at that time. If an investigator retires, moves or withdraws from an investigation, the responsibility for maintaining the records may be transferred to another person (sponsor, or other investigator) who will accept the responsibility, in concurrence with the Director of the Clinical Sciences Division, ICDDR,B.

The data specified in the protocol will be recorded in the CRF. Data should be clearly legible and recorded in black ballpoint pen. Where data are corrected, the original entry should be crossed out completely with a single line and completely rewritten. The person who amends the entry should initial and date the correction. The CRFs must be kept in order and up-to-date so that they always reflect the latest observations on the subjects enrolled in the study. CRFs must be completed legibly for each subject enrolled in the study and signed-off by the investigator. This should be done as soon as possible after completion of therapy. A monitor will review and collect the CRF.

Source documents must be maintained for all patients enrolled in the study. The source data is deemed to be the medium on which a parameter is originally recorded, e.g. case history notes. This source data must be made available to the Clinical Research Scientist or auditor for source data verification.

Personnel log detailing all staff involved in the study, will be kept in the Investigator file. This will contain an example of each individual's handwriting, what tasks they are permitted to carry out, and their job titles.

The investigator should maintain the individual subject files separate from the CRFs. The files should include visit dates of each subject, records of vital signs, medical history or examinations administered, laboratory results, concomitant treatment, any adverse event encountered and other notes deemed appropriate. This constitutes "source data". All entries on the CRFs must be backed up by source data.

Each subject's file should have attached to it the original signed Informed Consent. When the study treatment is completed, the Informed Consent should be kept on file with a copy of the completed CRF in the appropriate file folder provided, or a note made indicating where the records can be located. All records should be kept in conformance to applicable national laws, regulations and ICH requirements.

All original laboratory reports should be available for review in each subject's file. It is important that the original reports are available for review because of the possibility of inaccuracies or errors in transcribing data from original records to the CRF.

The investigator must agree to allow the Regulatory Authority representatives or members of the Local Ethics Committee (RRC &ERC) and Bayer representatives direct access to any trial related documents.

7.5 Premature termination of trial / closure of centre

If for any reasons the sponsor and the investigator together feel that this study should be terminated prior to its completion, an appropriate schedule and conditions for such termination will be instituted.

Reasons for premature termination of study:

- If a serious adverse event probably related to the drug administration occurs or if a significant change in the benefit-risk ratio for patients occurs, where continuation of the study would put the patients at undue risk.
- If the use of the study drug or one of its dosages becomes "no longer justifiable".

A premature termination of the study should be based on mutual agreement between investigator and sponsor.

In addition, Bayer may decide to close a centre prematurely for the following reasons:

- If there is clear evidence that the centre is unable to recruit at a reasonable rate as agreed at the outset of the study. As far as possible this should occur after mutual consultation.
- In case of obvious non-compliance with the protocol.

In the event of a study being discontinued prematurely, all study materials (completed, partially completed, and empty CRFs, study medication, etc.) must be returned to Bayer.

8. Adverse events

8.1 Adverse event monitoring

Each subject must be carefully monitored for adverse events. This includes clinical laboratory test variables. An assessment must be made of the seriousness, intensity and relation to the administration of the trial medication. In the event of an adverse event, the investigator will decide if the study will be continued or terminated for the patient. If treatment is required for management of a patient developing an adverse event, such treatment will be directed at the most prominent symptom. In the event of a serious adverse event, the study medication will be stopped, the patient will receive appropriate treatment, and the patients will be closely observed until reversal of the event and the patient has stabilised.

8.2 Adverse event definitions

Adverse event (AE)

Any adverse event associated with the use of a drug in humans, whether or not considered drug related, includes the following: an adverse event occurring in the course of the use of a drug product in professional practice; an adverse event occurring from an overdose whether accidental or intentional; an adverse event occurring from drug abuse; an adverse event occurring from drug withdrawal; and any failure of expected pharmacological action.

Serious adverse event

Includes an adverse event occurring at any dose that results in any of the following outcomes: death, a life-threatening drug experience, inpatient hospitalisation or prolongation of existing hospitalisation, a persistent or significant disability/incapacity, or a congenital anomaly/birth defect. Important medical events that may not result in death, be life-threatening, or require hospitalisation may be considered serious adverse drug events when, based upon appropriate medical judgement, they may jeopardise the subject and may require medical or surgical intervention to prevent one of the outcomes listed in this definition. Examples of such medical events include allergic bronchospasm requiring intensive treatment in an emergency room or at home, blood dyscrasias or convulsions that do not result in inpatient hospitalisation, or the development of drug dependency or drug abuse.

Life threatening means that the patient was, in the view of the investigator, at immediate risk of death from the reaction as it occurred. This does not include an AE that, had it occurred in a more serious form, might have caused death.

Disability means a substantial disruption of a person's ability to conduct normal life's functions.

In cases of overdose only events consequent to an overdose are reportable.

Unlisted (unexpected) adverse event

Any adverse drug experience, the specificity or severity of, which is not consistent with the current Investigators' Brochure (or Package Insert for marketed products).

Relation to investigational product

The assessment of the relationship of an adverse event to the administration of study drug (none, unlikely (remote), possible, probable, not assessable) is a clinical decision based on all available information at the time of the completion of the case report form.

None - includes: (1) the existence of a clear alternative explanation (e.g. mechanical bleeding at surgical site); or (2) non-plausibility (e.g., the patient is struck by an automobile at least where there is no indication that the drug caused disorientation that may have led to the event; cancer developing a few days after drug administration).

Unlikely (remote) - a clinical event, including lab abnormality, with an improbable time sequence to drug administration and in which other drugs, chemicals or underlying disease provide plausible explanation.

Possible - a clinical event, including laboratory abnormality, with a reasonable time sequence to administration of the drug, which could also be explained by concurrent disease* or other drugs or chemicals. Information on drug withdrawal may be lacking or unclear.

Probable - a clinical event including lab abnormality, with a reasonable time sequence to administration of the drug, unlikely to be attributed to concurrent disease* or other drugs or chemicals, and which follows a clinically reasonable response on withdrawal (dechallenge).

Not assessable - a report of an AE which cannot be judged because information is insufficient or contradictory, and which cannot be supplemented or verified.

* Concurrent disease includes concomitant, intercurrent and underlying disease/condition. Concomitant disease - any other illness the subject may have at the time of entering the clinical trial. Intercurrent disease - any other illness the subject may develop during the clinical trial. Underlying disease - the illness which is the indication for study drug therapy.

Factors to be considered include:

- **The temporal sequence from drug administration** (The event should occur after the drug is given. The length of time from drug exposure to event should be evaluated in the clinical context of the event.)
- **Recovery on discontinuation (dechallenge), recurrence on reintroduction (rechallenge)** (Subject's response after drug discontinuation (dechallenge) or subjects response after drug re-introduction (rechallenge) should be considered in the view of the usual clinical course of the event in question.)
- **Underlying, concomitant, intercurrent diseases** (Each report should be evaluated in the context of the natural history and course of the disease being treated and any other disease the subject may have.)

- **Concomitant medication or treatment** (The other drugs the subject is taking or the treatment the subject receives should be examined to determine whether any of them may be recognised to cause the event in question.)
- **Known response pattern for this class of drug** (Clinical/preclinical.)
- **Exposure to physical and/or mental stresses** (The exposure to stress might induce adverse changes in the recipient and provide a logical and better explanation for the event.)
- **The pharmacology and pharmacokinetics of the test drug** (The pharmacokinetic properties (absorption, distribution, metabolism and excretion) of the test drug (s) the subject is taking, coupled with the individual subject 's pharmacodynamics should be considered.)

Intensity (severity) of the event

The following classification should be used:

Mild: usually transient in nature and generally not interfering with normal activities.

Moderate: sufficiently discomforting to interfere with normal activities.

Severe: prevents normal activities.

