All patients who receive the study drug should be followed-up for 10 to 14 days after study entry. This should be done even if no adverse events or abnormal laboratory values are evident during hospitalisation. As indicated above, patients who develop any adverse event will be closely observed until the effect is reversed, or until a further change in the patient's condition is unlikely, and after a final causality assessment has been made. If a patient discontinues participation in the study for any reason, a final evaluation will be made at the time of discontinuation or as soon as possible thereafter. The results of the final assessment, and the reasons for discontinuation of study drug, will be recorded in the CRF. In the event of premature termination of study due to an adverse event, the procedure as described in Section 5.3 will be followed. Study patients presenting with adverse events, including clinically relevant laboratory

test abnormalities, will be followed-up by the investigator. Assessments must be made of the seriousness, intensity and relation to the administration of the trial medication.

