7. Physicians should abstain from engaging in research projects involving human subjects unless they are satisfied that the hazards involved are believed to be predictable. Physicians should cease any investigation if the hazards are found to outweigh the potential benefits.
8. In publication of the results of his or her research, the physician is obliged to preserve the accuracy of the results. Reports of experimentation not in accordance with the principles laid down in this Declaration should not be accepted for publication.
9. In any research on human beings, each potential subject must be adequately informed of the aims, methods, anticipated benefits and potential hazards of the study and the discomfort it may entail. He or she should be informed that he or she is at liberty to abstain from participation in the study and that he or she is free to withdraw his or her consent to participation at any time. The physician should then obtain the subject's freely given informed consent, preferably in writing.
10. When obtaining informed consent for the research project the physician should be particularly cautious if the subject is in a dependent relationship to him or her or may consent under duress. In that case the informed consent should be obtained by a physician who is not engaged in the investigation and who is completely independent of this official relationship.
11. In case of legal incompetence, informed consent should be obtained from the legal guardian in accordance with national legislation. Where physical or mental incapacity

makes it impossible to obtain informed consent, or when the subject is a minor, permission from the responsible relative replaces that of the subject in accordance with national legislation.

Whenever the minor child is in fact able to give consent, the minor's consent must be obtained in addition to the consent of the minor's legal guardian.

12. The research protocol should always contain a statement of the ethical considerations involved and should indicate that the principles enunciated in the present Declaration are complied with.

II. MEDICAL RESEARCH COMBINED WITH PROFESSIONAL CARE
(Clinical research)

1. In the treatment of the sick person, the physician must be free to use a new diagnostic and therapeutic measure, if in his or her judgement it offers hope of saving life, re-establishing health or alleviating suffering.

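### Section 8.2 makes response on withdrawal a condition of the *probable* causality grade; read literally, a single-dose ciprofloxacin event cannot meet it, and Section 7.5 relies on that grade

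*Protocol*

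**What the plan says.** Protocol Section 8.2 (Relation to investigational product) offers five grades: "none, unlikely (remote), possible, probable, not assessable". There is no *definite*, so *probable* is the top. Its definition joins three conditions: reasonable timing relative to dosing, an unlikely alternative cause, "and which follows a clinically reasonable response on withdrawal (dechallenge"). The grade below, *possible*, covers an event with reasonable timing "which could also be explained by concurrent disease* or other drugs or chemicals", and adds that "Information on drug withdrawal may be lacking or unclear". *Not assessable* is kept for reports whose information is insufficient or contradictory.

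Section 5.4 gives ciprofloxacin once and erythromycin every 6 hours for 3 days, 12 doses in all.

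Section 7.5 lists reasons for stopping the trial early. The first begins "If a serious adverse event probably related to the drug administration occurs". The same item offers a significant change in benefit-risk as an alternative, and a separate item covers use of the drug ceasing to be justifiable.

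**The concern.** A causality scale used to compare two drugs should let the same event, with the same timing and the same lack of another explanation, receive the same grade in either arm. Here the top grade depends on an observation that the regimen allows in one arm and not in the other. The trial is open and in children, and objective (ii) is comparative safety with emphasis on the musculoskeletal system, so the relation recorded for each event matters to whoever reads the safety data. Section 7.5 uses the same word for a termination ground, so the weakness in the definition carries into a trial-level rule.

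**Working it through.** No figure in the plan needs reproducing. The check sets the definitions in 8.2 against the regimens in 5.4 and the grounds in 7.5.

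1. **Is dechallenge necessary for *probable*?** Yes. The conditions are joined by *and*. The list of factors later in 8.2 describes dechallenge as recovery on discontinuation.

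2. **Can each drug be withdrawn after an event starts?** Ciprofloxacin: no, the course is complete after the first dose. Erythromycin: yes, while doses remain. From dose 1 to dose 12 there are 11 intervals of 6 hours, 11 × 6 = 66 hours. The arms can therefore differ only for events that start within about 66 hours of the first dose, and only where erythromycin is actually stopped.

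3. **Which grade fits an event with good timing and no other likely cause?**

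| Situation | *Probable* | *Possible* | *Not assessable* |
|---|---|---|---|
| Erythromycin, onset before dose 12, drug stopped, event recovers | fits | does not fit: no other explanation | does not fit |
| Ciprofloxacin, same onset, event recovers | literal reading: no, nothing was withdrawn | does not fit: no other explanation | does not fit: information is complete |
| Either drug, onset after the last dose | literal reading: no | does not fit | does not fit |
| Either drug, fatal or irreversible event | no: no recovery can occur | does not fit | does not fit |

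   Rows two to four fall into a gap. *Possible* tolerates missing withdrawal information, but it still describes an event that something else might explain.

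4. **Where do the arms differ?** Only between rows one and two. Joint findings first seen at the 10 to 14 day or 4 to 6 week visit come after all dosing in both arms, so they fall in row three or four and show no difference by arm.

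5. **What follows for 7.5?** Its event-specific ground needs a *probably* related serious event. Under the literal reading, a serious ciprofloxacin event cannot meet it, while a serious, reversible erythromycin event during dosing can. Sections 8.1 and 8.4 call for study drug to be stopped on a serious event, which creates the dechallenge observation in the erythromycin arm only.

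6. **Size.** With 90 children planned per arm, the literal reading allows 0 *probable* events among about 90 on ciprofloxacin, whatever the true rate. That is the limit of one reading, not a forecast.

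**The case against.** The strongest reply is that the literal reading is not the only one. Section 8.2 calls the assessment a clinical decision on everything known when the form is completed, and its list of factors includes pharmacokinetics, with excretion named. An investigator could treat recovery as a single dose is eliminated as the required response. The gap in the table is itself a hint that the literal reading was not intended. This stands as far as it goes: an event after ciprofloxacin might be graded *probable* in practice. But nowhere does the protocol say so, and two investigators could grade the same event differently.

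The second reply concerns consequences. Section 7.5 opens by letting sponsor and investigator end the study for any reason they agree on, and its benefit-risk and justifiability grounds do not use the causality scale. Section 9.5 plans descriptive summaries by body system, with no comparison by causality grade. Any new objective joint or gait finding is evaluated and followed up in both arms whatever its grade. All of this stands and limits what is at stake.

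Third, erythromycin does not always benefit. For non-serious events the investigator decides whether to continue, and without withdrawal and a response the condition fails there too.

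**Conclusion.** The definition of *probable* is badly fixed. As written, it can grade the same event differently by arm and leaves well-timed events with no other cause without a grade. It also makes the event-specific ground in 7.5 hardest to meet for fatal or irreversible events in either arm. This rests on reading withdrawal as the stopping of ongoing dosing, which is the natural sense of the text but not the only possible one. The matter is worth correcting because the correction is cheap. It changes no sample size, power or primary analysis.

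Three stronger conclusions might be inferred, and the documents do not support them:

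- **That a serious ciprofloxacin event could not end the trial.** The other grounds in 7.5 remain open.
- **That a planned comparison of drug-related events is biased.** The protocol plans none, and a count of *possible* and *probable* together would be much less exposed to the dechallenge clause.
- **That the stopping rule conflicts with the appended Declaration of Helsinki.** Section 7.5 says "A premature termination of the study should be based on mutual agreement between investigator and sponsor" and the Declaration says "Physicians should cease any investigation if the hazards are found to outweigh the potential benefits". The Declaration does not give that duty to the physician alone and describes its standards as guidance. Who may halt a trial is a question of governance, separate from this one.

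**What to change.** In Section 8.2, require the dechallenge condition for *probable* only where the drug could be withdrawn and the event is reversible. In all other cases allow *probable* on reasonable timing and absence of another likely cause. This closes the gap for single-dose, post-course, fatal and irreversible events, and applies equally to both arms.

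Reconcile the revised definition with the wording of the first ground in Section 7.5, so that it is clear the ground refers to the 8.2 grade and can be met in either arm.

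If drug-related events are tabulated by arm, define them as *possible* or *probable* together, which is how Section 6 already describes adverse reactions.

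The cost is a wording amendment to two sections. Slightly more ciprofloxacin events may be graded *probable*. No visit, measurement or analysis is added.

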8.3 Adverse event documentation

All adverse events occurring during the trial and follow-up period must be fully recorded in the subject's case record.

Documentation must be supported by an entry in the subject's file. Laboratory test abnormalities considered to be clinically relevant, e.g., causing the subject to drop out of the trial, requiring treatment, causing apparent clinical manifestations, or if the investigator believes the event to be relevant, should be reported as an adverse event. Each event should be described in detail along with start and stop dates, intensity, relationship to investigational product, action taken and outcome.

